## Study Synopsis

Study Title	Utilizing Holmium Laser for FURS Renal Stone Lithotripsy Comparing Stone Breaking vs. Stone Dusting Settings	
Protocol No:	LUM-SBU-VP-15-01	
Device Name:	Lumenis Pulse 120H Holmium Laser system	
Design	Prospective, randomized, single center	
Planned Study period	Initiation: January 2016	Final Report: May 2016
Objective	Primary: Demonstrate the efficiency of stone dusting Vs stone breaking of the P120H holmium laser and 200 DFL ball tip fibers Secondary: Demonstrate the usability and safety of stone dusting	
Study population	Twenty (20) subjects presenting with a renal stone and candidates for FURS	
Main Inclusion Criteria	

Subject will be older than 18 years of age

Subject was diagnosed with renal calculi between 0.8 to 2 cm in size

Subject is a candidate for FURS procedure

Subject is willing and has signed the Informed Consent Form

	
Main Exclusion Criteria	

Underwent previous PCNL or FURS in current kidney

Need to perform concomitant procedure, other than FURS

	
Investigational Treatment and study course	
A single FURS procedure will be performed with either high or low frequency holmium laser lithotripsy. Subjects will be randomized during enrollment to receive treatment with one of the two parameter sets.
 
Follow up sessions:
 

Day of discharge

One month follow-up

	
Criteria for Evaluation (endpoints)	
Primary Endpoints:
 

Procedure time

Usage of alternative stone extracting devices

Catheterization time

Time to hospital discharge

Stone clearance based on 1 month follow-up imaging data

 
Secondary Endpoints:
 

Intraoperative Complications – based on Modified Clavien Classification

Visibility during procedure

Occurrence of retropulsion that interferes with procedure

Ability to reach fragments during the procedure

Fiber flexibility with scope deflection- any damage to fiber

Fiber durability- deflection without losing energy/ efficiency

Damage to scope

	

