## 1.2 Rationale for Evaluation

The Lumenis Pulse P120H enables a wide range of working parameters that include use of high frequency at low energy. The use of the “stone dusting” set of parameters versus the commonly used “stone breaking” parameters may aid the physician in completing the procedure in a shorter period of time. The high frequency may reduce procedure time due to the ability to quickly fragment the stone, the resultant smaller stone fragments that can be washed out without the need for additional extraction procedures and the reduction of the retropulsion effect that necessitates repositioning of the flexible ureteroscope and fiber thus adding additional time to the procedure.

The 200 DFL fiber demonstrated high performances in terms of flexibility, efficiency and durability especially in high repetition rates. This fiber is considered to be Lumenis’s optimal solution for stone treatment in flexible ureteroscopy thus will be utilized in both procedures.

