## 6 Patient Population

### 6.1 Source and Sample Size

Subjects shall be selected by the physician within his patient population. One (1) site will participate in this study and will treat twenty (20) subjects. Enrolled subjects that did not complete the full course of the study will be discarded from performance analysis if they have not returned for the one month follow-up visits.

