## 7.3 Screening Procedures

### 7.3.1 Subject Enrollment

1. During the first visit, the investigator will screen the subject for eligibility to participate in the clinical study using the Inclusion, Exclusion criteria. During screening, the study physician will review the subject's medical history to ensure that the subject meets the study criteria.
2. If the subject has met the preliminary study eligibility criteria, the study physician will obtain an informed consent from the subject, clearly indicating his/her understanding of the procedure, requirements and risks involved with study participation and other applicable treatment options.
3. The subject will be enrolled to the study and the treatment will be scheduled.

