### 7.3.3 Subject randomization

Allocation of the treatment parameters used during the procedure will be performed using study randomized envelopes. The sponsor will provide the site with sealed envelopes containing "stone breaking" or "stone dusting" treatment parameters. Randomization will be divided into two groups of patients (1-10 and 11-20) with randomization ratio of 1:1 in each group. The randomization list will take into consideration additional subjects that will be required to replace subjects that have dropped from the study. If any subject drops out from the study and is replaced by another subject randomization will continue as per the original randomization scheme (this new subject will not receive the randomization of the subject that was replaced).

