### 7.6 FURS procedure

A flexible ureteroscope will be inserted over a guidewire to the kidney, with or without a ureteral access sheath, as needed. Renoscopy will then be performed and all calculi will be localized.

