#### 7.6.1 Fiber introduction

After the stones are visualized, the 200 DFL fiber is introduced through the scope (either partially deflected or fully deflected, till visible in the end of scope).

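### Randomization is placed at enrollment, earlier than the design needs, and nothing says when or by whom the envelope is opened

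*Combined protocol and SAP*

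**What the plan says.** **Timing.** The synopsis, under investigational treatment and study course, states: "Subjects will be randomized during enrollment to receive treatment with one of the two parameter sets". Section 7.3.1 lists the first-visit steps as screening, consent, and then: "The subject will be enrolled to the study and the treatment will be scheduled". Randomization is not itself one of the listed steps, and no maximum interval to surgery is set.

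**Mechanism.** Section 7.3.3 says: "The sponsor will provide the site with sealed envelopes containing 'stone breaking' or 'stone dusting' treatment parameters". It adds: "Randomization will be divided into two groups of patients (1-10 and 11-20) with randomization ratio of 1:1 in each group". It names neither the moment of opening nor the person who opens. A subject who drops out is replaced, and the replacement takes the next allocation on the list, not the lost subject's arm.

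**Operation.** Anesthesia, guidewire placement and any dilation come first (7.5). Section 7.6 then says: "Renoscopy will then be performed and all calculi will be localized". Section 7.6.1 continues: "After the stones are visualized, the 200 DFL fiber is introduced through the scope". The arm first matters in 7.6.2, where energy and frequency are set by group. The fiber does not distinguish the arms, since section 1.2 says it "thus will be utilized in both procedures".

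**Losses.** Section 6.1 states: "Enrolled subjects that did not complete the full course of the study will be discarded from performance analysis". The same sentence limits this to subjects who did not come back at one month. Section 10.4 lets the investigator or sponsor withdraw a subject at any time, and also asks that subjects be followed even when they cannot comply.

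**The concern.** Randomizing earlier than the treatment requires creates an interval in which subjects can be lost with an arm already assigned. Had the arm not yet been assigned, the same exits would be ordinary screen failures and could not affect the comparison.

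Two things are at stake in a trial of 20 with no blinding described. First, the analyzed subjects may differ from the randomized subjects. If the arm is known early, it could influence who is withdrawn. Second, an arm known before surgery could influence discretionary steps ahead of the laser. Some of that time may count in procedure time, a primary endpoint.

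**Working it through.** The documents give the sample size of 20 (6.1) without power, effect size, variability or dropout rate, so there is no stated figure to reproduce. The check is mainly one of sequence.

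**1. When the arm is assigned and when it is needed**

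| Step | Section | Depends on arm? |
|---|---|---|
| Screening, consent, enrollment; randomization per synopsis | 7.3.1, synopsis | Arm assigned here |
| Surgery scheduled | 7.3.1 | No |
| Anesthesia, guidewire, dilation | 7.5 | No |
| Sheath if used, renoscopy, stone localization | 7.5.4, 7.6 | No |
| Fiber introduction | 7.6.1, 1.2 | No, same fiber |
| Lithotripsy at assigned energy and frequency | 7.6.2 | Yes, first use |

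Nothing between the first and last rows requires the arm, and no section delays opening the envelope.

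**2. What can be lost in between.** A subject may withdraw, have surgery cancelled, or have failed access. The exclusion for a concomitant procedure in the same session (6.2.2.2) may become apparent only at surgery. Under the synopsis timing each is a post-randomization loss. If treated as a dropout, the subject is replaced under 7.3.3. Removal from the performance analysis under 6.1 follows only if the one-month visit is also missed.

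**3. Scale, on an assumed loss rate.** Let p be the proportion lost between randomization and laser use. For 20 randomized subjects, assuming independent losses, the expected loss is 20p and the chance of at least one is 1 − (1 − p)^20.

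| Assumed p | Expected loss | Chance of at least one |
|---|---|---|
| 5% | 20 × 0.05 = 1 | 1 − 0.95^20 = 64% |
| 10% | 20 × 0.10 = 2 | 1 − 0.90^20 = 88% |
| 15% | 20 × 0.15 = 3 | 1 − 0.85^20 = 96% |

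**4. What replacement does.** Suppose 10:10 are randomized and two subjects are lost from one arm, leaving 10:8. The next two allocations on the list can give 10:10, 11:9 or 12:8. Information on a difference in means is proportional to n1·n2/(n1 + n2): 100/20 = 5.00, 99/20 = 4.95 and 96/20 = 4.80. The worst of these costs 1 − 4.80/5.00 = 4%. Imbalance is therefore a minor cost. What replacement cannot do is restore the randomized set if losses depended on the arm.

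**5. Route through an arm known early.** Withdrawal at the investigator's or sponsor's discretion (10.4) is one route. Another is the choice of sheath (7.6) or type of anesthesia (7.5.1), which are left to need or hospital routine. Section 5.1 gives procedure time no start point, so these steps may be counted in it.

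**6. Predictability.** With 1:1 in each group of 10, each group holds five of each arm. Someone who knows nine allocations knows the tenth, and knows more once five of one arm have been used. This holds whenever the envelope is opened, and the remedy must allow for it.

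**The case against.** The order rests on one synopsis phrase read together with 7.3.1, which does not list randomization. The section on randomization itself leaves the moment of opening blank, so the sponsor may always have meant the envelope to stay sealed until surgery. That is a fair reading of intent, but no text says so, and the synopsis is the only statement of timing.

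A reader might go further and infer three things that the documents do not support:

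- **That the surgeon knows the arm when scheduling or choosing dilation and sheath.** This is possible but not documented. These steps are described as following need or hospital routine.
- **That section 6.1 discards everyone who does not reach lithotripsy.** Its condition is a missed one-month visit, and section 10.4 asks for continued follow-up.
- **That early losses break the randomized comparison.** Losses before any arm-specific treatment bias it only if they depend on the arm, and no dependence is shown.

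The strongest practical objection is that opening after renoscopy puts a surgeon's eligibility judgment just before allocation, when late allocations in a group of 10 can be guessed. That stands, and it calls for a safeguard. It does not favor the present timing, because the same sequence can be guessed at enrollment.

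**Conclusion.** The point holds as a design weakness that is cheap to remove. Allocation is earlier than the treatment requires, the moment of opening and the opener are unspecified, and concealment until the laser step is not provided for. The consequence is a set of avoidable post-randomization losses and an opening for arm-dependent decisions; the documents do not show that bias occurs.

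The size cannot be computed from the protocol. The figure of about 1 to 3 of 20 rests entirely on an assumed pre-laser loss of 5% to 15%. The timing conclusion rests on reading the synopsis and 7.3.1 together. If the sponsor intends later opening, the same wording change settles it.

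**What to change.** In the synopsis and section 7.3.3, state that:

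- the next sequentially numbered envelope is opened in the operating room by a staff member other than the surgeon;
- opening takes place after the stones have been localized and eligibility against the existing criteria has been recorded in writing, immediately before the laser is set;
- the time of opening is logged;
- every consented subject who leaves before opening is logged with the reason, as not randomized.

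Recording eligibility before opening, together with the log of earlier exits, is the safeguard against guessing late allocations within a group of 10; it makes selective exits visible but cannot rule them out.

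The cost is protocol wording, a short log and handling the envelope in theatre. No subjects or visits are added and no treatment changes. The change does not deal with missed one-month visits, which need their own analysis rule, or with the undefined start of procedure time, which needs a definition.

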## 1 Introduction

### 1.1 Background

The Lumenis Holmium Laser System family has been used for more than a decade for many procedures and specialties requiring excision, incision, ablation, and vaporization of tissue.

The holmium:yttrium–aluminum–garnet (Ho:YAG) laser, known as the holmium laser, is a very commonly used laser in urological surgery [1, 2]. Its wavelength of 2,120 nm is very near the absorption peak of water (1,910 nm). As a result, it can be used for soft tissue-based applications as well as stone fragmentation. Since soft tissue is comprised primarily of water, the holmium laser energy is effective for excision, incision, ablation, and vaporization when in direct contact with soft tissue, and for coagulation when a few millimeters from soft tissue. If fired directly onto mucosa, the laser has an effective penetration depth of 300– 400 micron, thus limiting the collateral injury during tissue-based applications. Additionally, stones (both urinary and gastrointestinal) contain sufficient amount of water that can absorb laser energy leading to their fragmentation, thus facilitating their removal [3].

Holmium laser energy is emitted using flexible hard core fibers of varying diameters to the target tissue. The flexibility of the fibers enables reaching and treating areas that otherwise would have been hard or impossible to reach.

The most common use of the holmium laser is for the fragmentation of urinary tract calculi (stones). Using rigid and flexible endoscopies the holmium fiber can be manipulated to reach stones located within the lower and upper regions of the urinary tract, including the renal pelvis [4, 7]. Once placed in the correct location the holmium laser is capable of fragmenting any type of stone. Comparison of this technique to external energy sources such as extracorporeal shockwave energy shows a clearly significant difference in stone fragmentation, favoring laser lithotripsy both for the absolute ability to fragment stones and the required number of sessions for complete removal [5]. Complications are minimal and transient [5]. Holmium laser lithotripsy has recently also been shown to be a safe and effective method for the management of large renal stones (2-3 cm) [6]. When the laser is combined with suction, large renal stone removal surgery can also be safe and effective, while decreasing the total operative time [13].

Due to its flexibility advantage, holmium lithotripsy is mostly described as the modality of choice for retrograde ureteroscopic fragmentation of ureteral stones and small renal stones. During these procedures low power settings (low energy and frequency) are commonly used, due to the retropulsion effect of the holmium laser on the stone that prolong the lithotripsy process. These low power settings limit the fragmentation efficacy of the laser.

Several methods to overcome retropulsion have been shown in in-vitro testing, including reduced energy per pulse used at higher frequencies and longer pulse duration [8, 9, 10]. The use of high

frequency (40-80Hz) at low energy settings (0.2-0.5) has been suggested to enable fragmenting the stone into very fine particles (dust) that are washed out spontaneously. The use of decreased energy per pulse minimizes retropulsion, whereas the use of high frequency enables the application of the same accumulated energy to the stone, thus leading to similar lithotripsy. The application of these parameters in a clinical scenario has been limited, but explorative studies have shown that the use of stone dusting settings with high frequency & low energy can reduce operative time while demonstrating excellent clearance of renal stones at one month post procedure [14]

## 1.2 Rationale for Evaluation

The Lumenis Pulse P120H enables a wide range of working parameters that include use of high frequency at low energy. The use of the “stone dusting” set of parameters versus the commonly used “stone breaking” parameters may aid the physician in completing the procedure in a shorter period of time. The high frequency may reduce procedure time due to the ability to quickly fragment the stone, the resultant smaller stone fragments that can be washed out without the need for additional extraction procedures and the reduction of the retropulsion effect that necessitates repositioning of the flexible ureteroscope and fiber thus adding additional time to the procedure.

The 200 DFL fiber demonstrated high performances in terms of flexibility, efficiency and durability especially in high repetition rates. This fiber is considered to be Lumenis’s optimal solution for stone treatment in flexible ureteroscopy thus will be utilized in both procedures.

## 2 Device Description

### 2.1 Laser System – Lumenis Pulse P120H Holmium Laser

The Lumenis Pulse P120H is a high pulsed solid-state laser used for Urology procedures, worldwide. Importantly, both intended use and indications for use claims as well as underlying laser technology are similar to the marketed product. The activated laser is based on a flash lamp excited, Ho:YAG rod. The Ho:YAG rod derived photons are guided into the attached delivery system fiber. The system delivers a second, low powered laser in the visible wavelength spectrum of 650nm that enables aiming the high, invisible laser energy to the desired location.

### 2.2 Fiber

Slimline end-firing silica fibers are standard fibers used for laser lithotripsy procedures, to deliver laser energy from the system to the treatment site. The new 200 DFL flexible fiber is specially designed with a ball tip to facilitate fiber introduction through a fully deflected ureteroscope. The Slimline 200 micron fiber is single use, supplied ethylene oxide sterile.

[figure not shown]

Figure 1 - 200 micron fiber with ball tip

### 3 Study Design

This is a randomized, two arms, prospective, single center study. Subjects will undergo a single flexible ureteroscopic renal surgery (FURS) procedure for a kidney stone as part of this study, using the study device. Follow up visits are scheduled for the day of release from the hospital and at 1 month post procedure. Additional treatment sessions, if required, will be at the discretion of the investigator, as part of the site standard of practice. Additional treatment sessions will not be included in this study.

### 4 Study Objectives

#### 4.1 Primary

Demonstrate the efficiency of stone dusting Vs stone breaking of the P120H holmium laser and 200 DFL ball tip fibers

#### 4.2 Secondary

Demonstrate the usability and safety of stone dusting

### 5 Outcome Measures

#### 5.1 Primary Endpoints

- Procedure time
- Usage of alternative stone extracting devices
- Catheterization time
- Time to hospital discharge
- Stone clearance based on 1 month follow-up imaging data

## 5.2 Secondary Performance Endpoints

- Intraoperative Complications – based on Modified Clavien Classification
- Visibility during procedure
- Occurrence of retropulsion that interferes with procedure
- Ability to reach fragments during the procedure
- Fiber flexibility with scope deflection- any damage to fiber
- Fiber durability- deflection without losing energy/ efficiency
- Damage to scope

## 5.3 Safety

Incidence and severity of adverse events will be based on the modified Clavien classification system [12]

## 6 Patient Population

### 6.1 Source and Sample Size

Subjects shall be selected by the physician within his patient population. One (1) site will participate in this study and will treat twenty (20) subjects. Enrolled subjects that did not complete the full course of the study will be discarded from performance analysis if they have not returned for the one month follow-up visits.

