#### 7.2.1 Objective Measures

- 7.2.1.1 Blood workup: including CBC & BMP
- 7.2.1.2 Urine workup: including urine analysis and urine culture (if applicable)
- 7.2.1.3 Renal stone size and location will be performed using Computer Tomography
- 7.2.1.4 All imaging verifying the diagnosis, pre-intervention images, intra-operative (during laser activation) images, immediate post-operative and follow-up images and relevant fluoroscopy and CT images will be recorded on electronic media for documentation, further analysis and data recording.  
Subject anonymity will be assured for all images by deleting any ID detail. Only the code for the Case Number in the study will appear on the records being transferred to the sponsor.
- 7.2.1.5 Stone clearance status will be confirmed one month post discharge using non contrast abdominal Computed tomography (for Radiolucent calculus) or KUB X-ray combined with kidneys and bladder Ultrasound imaging (for radiopaque calculus).

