#### 7.2.2 Investigator Subjective Assessments

- 7.2.2.1 Procedure Questionnaire will record subjective usability parameters such as ability to maintain fiber durability and deflection, retropulsion and visibility impairment and resolution (due to bleeding or other disturbances), subjective assessment of lithotripsy efficiency, aspiration and combined procedures.

- Intraoperative Complications – based on Modified Clavien Classification

Table 1 – Assessments time-points

Assessment	Performed During Visit			
	Baseline (Pre-operative)	Perioperative	Hospital discharge	1 month follow- up
Subject assessment (ICF, medical history, demographics, inclusion/exclusion evaluation)	X			
Imaging	X (CT and / or X-ray)			X (CT and / or X-ray)
Blood analysis (CBC & BMP) and urine analysis	X		X	X
Urine culture (if applicable)	X			X
Physician Subjective Procedure questionnaire		X		
Adverse Event Assessment		X	X	X

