#### 7.6.3 Stone clearance

In all stages of the procedure, stone fragments extraction may be assisted, if needed by the use of baskets, forceps or saline flushing. Use of such accessories will be recorded.

At the end of stone fragmentation procedure, the renal pelvis will be inspected again and a "stone-free status" will be determined by the surgeon. Remnant fragments of 1 mm will be included under the "stone-free status" category. Complete stone clearance will be confirmed by intraoperative fluoroscopy. Finally, the ureter will also be inspected ureteroscopically and fluoroscopically with the administration of contrast medium to detect possible urine extravasation and remnant stone fragments.

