## 8 Study Analysis Plan

### 8.1 Study Analysis

The results of the study: subject demographics, baseline assessments, treatment parameters, treatment evaluations and follow-up assessments will be summarized and descriptive analysis will be performed. Continuous variables will be compared between the two groups using independent samples Student's t-test or Mann-Whitney U test. A p-value < 0.05 will be considered as significant.

Adverse events reported will be listed, documenting course, outcome, severity, and possible relationship to the treatment. The modified Clavien classification will be used to evaluate severity of Adverse Events [12].

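### The 6.1 exclusion of subjects who miss the 1-month visit is not limited to stone clearance, so it can remove operative outcomes already recorded for treated subjects

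*Combined protocol and SAP*

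**What the plan says.** Section 6.1 plans 20 treated subjects and states that those who do not complete the study "will be discarded from performance analysis if they have not returned for the one month follow-up visits". What is discarded is the subject, not the missing value. The name given to that analysis appears nowhere else.

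The endpoints are in section 5:

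- 5.1 lists five primary endpoints: procedure time, use of extraction devices, catheterization time, time to discharge, and "Stone clearance based on 1 month follow-up imaging data".
- 5.2 lists seven further endpoints, all about the operation, under the heading "Secondary Performance Endpoints".
- 5.3 lists safety separately.

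On data collection, 7.2.1 says "Stone clearance status will be confirmed one month post discharge using non contrast abdominal Computed tomography", or by X-ray with ultrasound, depending on stone type. Most 5.2 items come from the operation itself: "Procedure Questionnaire will record subjective usability parameters" (7.2.2). For extraction devices, 7.6.3 says "Use of such accessories will be recorded".

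On analysis, 8.1 says that "treatment evaluations and follow-up assessments will be summarized and descriptive analysis will be performed". It names t-test or Mann-Whitney comparisons for continuous variables, but no analysis population and no missing-data rule. Section 8.2 plans an interim look at immediate post-operative data once at least 10 subjects have been operated on. On dropouts, 7.3.3 says "If any subject drops out from the study and is replaced by another subject randomization will continue as per the original randomization scheme". Section 10.4 keeps the records of early terminators, asks for reasonable contact effort, and lists an adverse event that prevents compliance among the possible reasons for dropout.

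**The concern.** A subject who was operated on, discharged and then missed one visit has a known procedure time, known device use and a completed procedure questionnaire. A rule that removes the whole subject discards those values for a reason unrelated to whether they were observed. Two analysts could also build different analysis sets from the same sentence.

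The stake is selection. With 10 subjects per arm, each one excluded is 10% of an arm. If non-return is related to how surgery or recovery went, and differs between arms, the operative comparison is no longer between the groups as randomized. Section 10.4 itself foresees dropout because of an adverse event, so a link to outcome cannot be assumed away.

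**Working it through.** The plan gives no figure to reproduce: 20 subjects is stated without effect size, SD, power or non-return rate. The check is first textual, then an illustration under stated assumptions.

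**1. What each reading removes, per treated non-returner**

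| Reading of the 6.1 exclusion | Observed endpoints removed |
|---|---|
| A. Stone clearance only | 0 |
| B. The 5.2 endpoints | 7 (6 if intraoperative complications are counted as kept through the adverse event listings) |
| C. Primary and 5.2 endpoints | 7 + 3 = at least 10 of 12 (9 with the same allowance) |

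The 3 added under C are procedure time, device use and time to discharge. Catheterization time is left out of the count because it is undefined and could run past discharge if a stent stays in. A subject who drops out after enrolment but before surgery has no operative values to lose, so the counts apply to treated subjects only.

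**2. Which reading the text favours**

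The word in question heads 5.2, and safety follows under its own heading in 5.3. That points most directly to B. Because the 5.2 heading begins with Secondary, the 5.1 list can be read as the primary performance endpoints, which gives C. Reading A needs a limit that 6.1 does not state.

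**3. Illustration under reading C: procedure time**

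Assumptions: normal outcome, no true difference, 10 per arm (1:1 under 7.3.3), one arm loses 2 of 10, two-sided 0.05 (8.1 does not state sidedness).

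Expected shift in the depleted arm's mean: the expected values of the five largest of 10 standard normal observations are about 1.539, 1.001, 0.656, 0.376 and 0.123 (sum 3.695), and all 10 sum to zero. So:

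- Two longest lost: −(1.539 + 1.001)/8 = −0.318 SD. If replaced by two new subjects, the divisor is 10: −0.254 SD.
- Two lost at random from the longer half: −2 × (3.695/5)/8 = −0.185 SD. If replaced: −0.148 SD.

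Test: T = (mean₁ − mean₂) / [s_p √(1/n₁ + 1/n₂)] on n₁ + n₂ − 2 degrees of freedom, and the exact Mann-Whitney test. Type I error from 400,000 simulated trials (Monte Carlo SE at most 0.05 percentage points):

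| Loss in one arm | t-test | Mann-Whitney |
|---|---|---|
| None | 5.0% | 4.3% |
| 2 at random | 5.0% | 4.3% |
| 1 from the longer half | 5.0% | 4.3% |
| 2 from the longer half | 6.0% | 5.2% |
| 2 from the longer half, replaced | 5.7% | 5.0% |
| 2 longest (extreme) | 11.6% | 10.3% |
| 2 longest, replaced | 10.0% | 8.6% |

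Replacement restores the numbers and dilutes the shift by the factor 8/10, but does not remove it.

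**4. Reading B**

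The 5.2 items read as categorical or subjective, and 8.1 names between-group tests for continuous variables only. The error rates above therefore have no planned test to attach to. The effect is mainly a smaller and possibly selected denominator. As a purely hypothetical case, an item present in 3 of 10 subjects (30%) would be reported as 1 of 8 (12.5%) if two of those three did not return.

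**The case against.** The strongest defence is that the sponsor meant stone clearance only. Section 7.7 says the 1-month visit is for assessing stone clearance and well-being, and the 8.2 interim analysis uses operated subjects with no 1-month condition. Both show some separation between operative data and the later visit, so reading A cannot be ruled out. But neither passage governs the final comparison, and 8.1 names no population. A subject could be counted at the interim and be missing at the end. Keeping records under 10.4 is not the same as analysing them.

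Three stronger inferences are tempting and should not be drawn.

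- A reader might conclude that the whole efficacy comparison is completers-only. For the primary endpoints other than stone clearance, that holds only under C, whereas the 5.2 heading points first to B.
- A reader might take the 11.6% as the expected inflation. It needs the two longest cases to be lost, both in one arm. One loss from the longer half gives no inflation, and two give about one percentage point. The contact effort in 10.4 should also keep losses down.
- A reader might infer a loss of power. Without replacement, the difference detectable with 80% power (a target the documents do not set) would rise from 1.32 SD at 10 v 10 to 1.41 SD at 9 v 9. But 7.3.3 provides for replacing dropouts.

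What stands is the unlimited, undefined exclusion and the possibility of outcome-related loss.

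**Conclusion.** The concern holds as a defect in the analysis rule that should be fixed, not as a demonstrated bias. Confidence is high that the term is undefined, that no endpoint limit is stated, and that no passage returns non-returners to the final comparison. It is moderate that B or C is what an analyst would apply.

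The number of subjects affected is unknown; assumed non-return of 5%, 10% or 20% would mean 1, 2 or 4 of 20. Any distortion depends on non-return being related to outcome and differing between arms. Under C it ranges from nil to about 1 percentage point of type I error with mild selection, and to about 6.6 points (11.6% − 5.0%) in the extreme case. Under B it is a matter of denominators in descriptive tables. Under A no observed value is lost.

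**What to change.** Replace the 6.1 sentence with:

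> All randomized subjects who undergo the procedure are analysed in their randomized group for every endpoint observed, whether or not they return at 1 month. Only stone clearance (and any endpoint not complete without that visit) is treated as missing for non-returners, under a missing-data rule fixed before outcomes are seen, with a sensitivity analysis.

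The missing-data rule is for the sponsor to choose. Section 8.1 should refer to this population. Section 7.3.3 should state that treated subjects who are replaced stay in the analysis.

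The cost is protocol wording and a little more analysis work, with no extra subjects or data. The downside is unequal denominators across endpoints, so each table should show its own n.
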